6.4. Covariates and Subgroups

Clinical and therapeutic cure will be analyzed by subgroup. Subgroups will be defined by first time or recurrent BV infection as defined in Section 3.3. Additionally, subjects with *Candida spp.* identified at screening will be analyzed to evaluate quantitative changes of *Candida spp.* See Section 8.3 for more details on the exploratory efficacy analyses.

6.5. Missing Data

Subjects who are non-evaluable for clinical cure at the TOC visit will be excluded from the PP population. Non-evaluable therapeutic cures will be handled similarly for the PP population. For the mITT, ITT, and Evaluable analysis populations, the cure status of subjects whose status cannot be determined at the TOC visit for any reason will be considered 'not cured' or failure for all cure-related endpoints. The cure status of subjects whose status cannot be determined at Visit 3 for any reason will be imputed using Last Observation Carried Forward (LOCF). Note this differs from what is stated in Section 11.3 of the protocol. See Section 12 for more details.

A sensitivity analysis will be performed to assess the impact of missing results on the primary efficacy outcome. The primary analysis will be repeated in which subjects in the 5% Monolaurin Vaginal Gel arm who are not evaluable for clinical cure will have their cure status imputed as a clinical failure and subjects in the placebo arm who are not evaluable for clinical cure will have their cure status imputed as a clinical cure. See **Table 56**.

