#### **Current Treatments**

The Centers for Disease Control and Prevention (CDC) recommends metronidazole 500 mg orally twice daily for 7 days, intravaginal metronidazole gel 0.75% once daily for 5 days or clindamycin cream 2% intravaginally once daily for 7 days as first line therapy for BV [9].

Alternative regimens using oral tinidazole, oral clindamycin or clindamycin ovules are also provided. However, up to 30% of women will have recurrent BV within 3 months of therapy [13]. Frequent emergence of vaginal candidiasis results from antibiotic suppression of vaginal flora, and *Candida species* are frequent commensal organisms in vaginal flora. Given BV's high recurrence rates and the risks for antimicrobial resistance, additional treatment options are desirable.

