- Subjects will be counseled to come in for an unscheduled visit if their vaginitis symptoms recur/worsen between Visit 2 and 3.
- Document Investigator assessment of clinical cure.

If the signs and symptoms of BV fail to resolve and further treatment is required (in the Investigator's opinion), the subject will be referred to her provider for standard treatment. Therapy will be recorded on the appropriate source document and electronic CRF (eCRF) pages and the subject will be followed through Visit 3 for safety. At Visit 3, these subjects will be classified as a clinical failure.

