Subjects who are non-evaluable for clinical cure at the Test of Cure visit are excluded from the PP population, but included in the mITT, ITT, and Evaluable populations as treatment failures. Last Observation Carried Forward will be used as a sensitivity analysis. Non-evaluable therapeutic cures will be handled similarly.

>3

Not Evaluable

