12. SUMMARY OF CHANGES IN THE CONDUCT OF THE STUDY OR PLANNED ANALYSES

Protocol version 5.0 (August 31, 2016) changed the criterion requiring all four Amsel criteria for inclusion to any 3 of 4 Amsel criteria; changed the allowable interval between a previous vaginal/cervical/pelvic infection or episode of BV from 60 days prior to enrollment to 14 days and removed the prohibition of systemic, vaginal or perineal immunosuppressant or antiinflammatory medications within 14 days of treatment; and changed the procedure for review of the Gram stain when two independent reviewers have different Nugent scores. Protocol version 6.0 (November 29, 2016) included the addition of a clinical site, Duke University, and clarification of temperature range for specimen storage. Protocol version 7.0 (May 11, 2017) removed the criterion requiring subjects over age 21 to report a normal PAP smear within the past 3 years, revised the exclusion for HPV and cervical or vaginal dysplasia to exclude only HSIL, AGUS, or CIN2 or higher, changed exclusions for previous self-treatment for yeast vaginitis and systemic, vaginal, or perineal antibiotics from 14 days to 7 days, and removed exclusion for 6 or more episodes of vaginitis within the past year, clarified that subjects found to have HSIL or AGUS at visit 1 will have study treatment discontinued and subjects found to have HSIL, AGUS, or CIN2 or higher at visit 1 will be excluded from the PP analysis population, and corrected protocol deviation plan such that sexual intercourse 48 hours prior to Visit 3 will not exclude subjects from the Per-Protocol data analysis population definition. Protocol version 8.0 (May 23, 2017) removed exclusion for diabetes.

Protocol Section 11.3 states Last Observation Carried Forward (LOCF) will be used as a sensitivity analysis. Section 6.5 of this analysis plan clarifies that LOCF will be used to impute the cure status of subjects whose status cannot be determined at Visit 3 for any reason. Subjects whose status cannot be determined at the TOC visit, will be considered 'not cured' for all cure-related endpoints.

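### Visit 3 cure rests on last observation carried forward alone, with no labelled sensitivity analysis of its no-relapse assumption

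*SAP*

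**What the plan says.** SAP 6.5 has two rules for undetermined cure status in the mITT, ITT and Evaluable populations. At the Test of Cure visit (Visit 2) such subjects "will be considered 'not cured' or failure for all cure-related endpoints". For the final visit: "The cure status of subjects whose status cannot be determined at Visit 3 for any reason will be imputed using Last Observation Carried Forward (LOCF".

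Protocol 11.3 assigns LOCF a different role. Subjects non-evaluable at the Test of Cure visit are "included in the mITT, ITT, and Evaluable populations as treatment failures", and then: "Last Observation Carried Forward will be used as a sensitivity analysis". SAP 6.5 acknowledges that it departs from protocol 11.3. SAP Section 12 describes the step more mildly, saying that Section 6.5 "clarifies that LOCF will be used to impute the cure status of subjects whose status cannot be determined at Visit 3 for any reason", and gives no reason for it.

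The SAP plans one missing-data check: "A sensitivity analysis will be performed to assess the impact of missing results on the primary efficacy outcome". Its shell, Table 56, is for clinical cure at Visit 2 in mITT. Tables 30 and 32 (clinical and therapeutic cure at Visit 3) and the Visit 3 subgroup Tables 49-50 and 53-54 have no counterpart.

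**The concern.** Visit 3 cure is a secondary outcome and the trial's only look at whether an early response lasts. Carrying a Visit 2 cure forward assumes that no woman without later information has relapsed. The protocol itself expects relapse. Its section on current treatments says that "up to 30% of women will have recurrent BV within 3 months of therapy", and section 7.2 provides that "Subjects will be counseled to come in for an unscheduled visit if their vaginitis symptoms recur/worsen between Visit 2 and 3". A carried-forward failure stays a failure, so compared with counting missing as not cured, LOCF can only add cures. It adds more of them in the arm with more Visit 2 cures. The Visit 3 estimates and intervals in the three main efficacy populations therefore rest on one assumption that no planned, labelled analysis tests.

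**Working it through.** **1. Inputs.** The documents give no Visit 3 missingness, no relapse rate by Day 22-31 and no expected cure rates. As an anchor I take one cell of the power table (protocol Table 4, SAP Section 5): cure .50 versus .20 with 60 and 30 women, stated power .78. Full enumeration of the two-sided Fisher's exact test gives 0.783, so that cell reproduces. It concerns the Visit 2 test and is used here only for the cure rates and arm sizes. Assumed: share missing at Visit 3, m = 5-20%; relapse among Visit 2 cures, r = 10-30%. The upper end of r borrows the protocol's three-month figure. The gap between the visits is only 7 days (Day 15 to Day 22) to 23 days (Day 8 to Day 31), so 30% is a high value.

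**2. Formulas.** With Visit 2 cure p and late cure s among Visit 2 failures, and data missing at random:

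- True Visit 3 rate: T = p(1 - r) + (1 - p)s
- LOCF: (1 - m)T + m·p
- Missing = not cured: (1 - m)T

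With m, r and s equal in both arms, LOCF bias in the difference is m(r + s)(pT - pC), where pT and pC are the active and placebo Visit 2 cure rates.

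**3. LOCF bias in the difference, s = 0** (m × r × 0.30, in percentage points):

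| m | r = 10% | r = 20% | r = 30% |
|---|---|---|---|
| 5% | 0.15 | 0.30 | 0.45 |
| 10% | 0.30 | 0.60 | 0.90 |
| 20% | 0.60 | 1.20 | 1.80 |

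By arm the excess is m × r × p: 0.25 to 3.0 points on active (.05 × .10 × .50 to .20 × .30 × .50) and 0.1 to 1.2 on placebo.

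**4. Both rules against the same truth, m = 20%, r = 30%, s = 0:**

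| | Active | Placebo | Difference | Bias |
|---|---|---|---|---|
| Truth | .35 | .14 | 21.0 | |
| LOCF | .38 | .152 | 22.8 | +1.8 |
| Missing = not cured | .28 | .112 | 16.8 | -4.2 |

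The rules differ by m(pT - pC): 1.5 points at 5% missing, 3.0 at 10%, 6.0 at 20%.

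**5. Departures from these assumptions.**

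- Every missing Visit 2 cure has relapsed: the truth equals missing = not cured, so LOCF is off by +3.0 points at m = 10% and +6.0 at m = 20%.
- Late cure s = 10%, with r = 30% and m = 20%: the true difference is .40 - .22 = 18.0 points and LOCF gives .42 - .216 = 20.4, a bias of +2.4. The placebo rate itself is slightly understated.
- Missing 5% active versus 20% placebo, r = 30%: .05 × .30 × .50 - .20 × .30 × .20 = .0075 - .0120, or -0.45 points.
- Relapse 10% active versus 30% placebo, m = 20%: .20 × (.10 × .50 - .30 × .20) = -0.2 points.

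**6. In counts (constructed, m = 20%).** Missing = not cured: 17/60 versus 3/30, difference 0.183, 95% Newcombe interval -0.001 to 0.324. LOCF: 23/60 versus 4/30, difference 0.250, interval 0.052 to 0.400. The rule alone can decide whether the interval includes zero.

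**The case against.** The strongest defence is that LOCF may be the better single rule. With equal missingness and relapse and no late cures, its bias in the difference is +m·r·(pT - pC), against -m·(1 - r)·(pT - pC) for missing = not cured. LOCF is therefore closer to the truth unless more than half of the missing early cures relapsed. That stands, and it is why simply replacing LOCF is not recommended.

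A reader might infer that the SAP overturns an explicit protocol rule for Visit 3. The text does not support this. The failure rule in protocol 11.3 names only the Test of Cure visit, and no main rule for missing Visit 3 status is stated. LOCF at Visit 2 would normally carry forward baseline disease, which is failure anyway, so the protocol's LOCF sensitivity analysis has content mainly at Visit 3. The mismatch that remains is one of role: a sensitivity analysis became the only analysis. Nor was the departure hidden, since SAP 6.5 acknowledges it.

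A reader might also infer that every early cure who fails to return is scored as cured. That is too broad. Under SAP 3.3.3, other vaginosis or systemic antimicrobial therapy, or an investigator's judgement that more treatment is needed, is already failure. Early termination visits include a cure assessment, and women are advised to return if symptoms recur. The assumption falls only on women with no later information.

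Finally, some non-LOCF information is planned. The Visit 3 per-protocol population generally requires attendance at Visit 3, and Table 45 has a Not Evaluable column at Visit 3 for ITT. Both views are indirect. The first selects attenders, and the second is a Nugent cross-tabulation rather than a cure comparison with an interval.

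**Conclusion.** The point holds as a gap in the Visit 3 analysis. LOCF is the sole rule in mITT, ITT and Evaluable, it assumes no relapse among women without later information, and no labelled Visit 3 analysis tests that. Under the assumed .50 versus .20, 5-20% missing and 10-30% relapse, equal in both arms and with no late cures, the overstatement is modest at 0.15 to 1.8 points. It reaches 6.0 points only if all missing early cures relapsed at 20% missing.

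Two stronger readings should be resisted. The 6.0-point gap between the two rules at 20% missing is not in general the bias of LOCF; it equals the bias only in that extreme case. And LOCF does not always favour the arm with more early cures: the sign turned in two of the unequal-arm cases, and there is no bias in the difference if Visit 2 cure, missingness, relapse and late cure are equal across arms. The affected outcomes are secondary or exploratory and are reported as estimates with intervals, without a planned test. The primary Visit 2 analysis is untouched.

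**What to change.** In SAP 6.5 and Tables 30 and 32, and in the Visit 3 subgroup Tables 49-50 and 53-54, report Visit 3 cure under both missing = not cured and LOCF, each labelled as such. Extend the Table 56 imputation (active missing as failure, placebo missing as cure) to Visit 3. In Section 12, state that making LOCF the Visit 3 rule changes its role from protocol 11.3, and give the reason.

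No new data are needed, and the cost is a few tables. The downside is a wider stated range for the Visit 3 outcomes. In the 20% missing, 30% relapse example, the Table 56 rule would give .28 versus .112 + .20 = .312, a difference of -3.2 points, against 16.8 under missing = not cured and 22.8 under LOCF. The Table 56 result is a deliberate extreme and should be presented as a bound rather than an estimate.

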6.6. Interim Analyses and Data Monitoring

The study is monitored to determine if any of the safety halting rules are met.

Enrollment will be halted for DSMB review/recommendation if any of the following are reported:

- 1. One or more subjects experiences a treatment-related SAE.
- 2. One or more subjects experiences vulvar and/or vaginal ulceration, abscess, or necrosis associated with study product administration.
- 3. Two or more subjects experience a treatment-related severe (Grade 3) unsolicited adverse event.
- 4. Three or more subjects who received at least one treatment dose experience the same severe (Grade 3) solicited AE as evaluated by a licensed clinician.
- 5. Three or more subjects who received at least one treatment dose experience a severe (Grade 3) study-related laboratory abnormality in the same laboratory parameter.
- 6. An overall pattern of symptomatic, clinical, or laboratory events that the DMID, Medical Monitor, or DSMB consider associated with study product and that may collectively represent a serious potential concern for safety.

If any of the halting rules are met, the study will not continue with the remaining enrollments or study treatments without a review by and recommendation from the DSMB to proceed. A summary of halting rules is provided in **Table 85**.

The DSMB met after 30 subjects received at least one dose of study drug and completed Visit 2. The DSMB will also review study progress and subject safety data at least annually during the course of the study and will hold a study closeout meeting 6 to 8 months after database lock, as defined in the DSMB Charter. The DSMB may also meet for an ad hoc review in response to a safety issue.

Additionally, a single, fully blinded interim analysis took place to reassess the adequacy of the sample size based on subjects meeting eligibility for the mITT population. After eighty subjects were enrolled and had available baseline test results for Nugent score, HIV, chlamydia and gonorrhea, the fraction of subjects enrolled to date who were eligible for the mITT cohort was estimated. Based on this calculation, the enrollment target was not increased from 120 subjects. The study sponsor and investigators had access to the data shared in fully blinded reports issued to the DSMB. The tables and figures for the interim analysis are contained in the DSMB Interim Analysis Safety Summary Report.

6.7. Multicenter Studies

Safety and efficacy data will be pooled across all clinical sites. Center effects are not anticipated because treatment is self-administered, the sites are using standardized procedures for assessment of unsolicited adverse events, and the study relies on a central laboratory for Gram stain Nugent scoring. See Sections 8.3 and 9.3 for more details.

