## PROTOCOL SUMMARY

A Phase II, Double-Blind, Randomized, Placebo-Controlled, Multicenter Trial to Assess the Safety and Efficacy of

5% Monolaurin Vaginal Gel Administered

Intravaginally for the Treatment of Bacterial Vaginosis

Phase: II

120 women, 18-50 years old, with clinical evidence of bacterial vaginosis, recruited from the community around the University of

Iowa Hospitals and Clinics, Cincinnati Children's Hospital Medical Center and Duke University School of Medicine.

Number of Sites: 2

**Study Duration:** 13 months

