#### 7. STUDY SCHEDULE

# 7.1. Screening and Enrollment (Visit 1, Day 1)

Subjects should be scheduled for visits when they are not menstruating and instructed to avoid inserting any substance into the genital tract for 48 hours before examination at Visit 1, when possible. Subjects may present after having clinical evaluation by a non-study clinician or may present to the research clinic directly.

The following procedures will be performed:

- Obtain signed informed consent. This should be performed prior to conducting any of the assessments listed below.
- Review inclusion/exclusion criteria and collect demographic information.
- Obtain medical history and concomitant medications (prescription and over-the-counter drugs, supplements, and vitamins taken 30 days prior to enrollment will be reviewed and documented).
- Review of contraceptive methods and recent menstrual history.
- Review sexual history.
- Review subject report of history of previous episodes of BV and if noted, the number of episodes of BV in the previous 12 months and treatments given.
- Assessment of current symptoms of BV
- Perform physical exam.
- Perform urine pregnancy test for female subject of childbearing potential prior to pelvic exam. Must be negative prior to receipt of study drug.
- Gynecologic exam for evaluation of the cervix, vagina, and vulva:
  - Assessment for genital tract infections and lesions. If evidence of active lesions
    consistent with herpes simplex virus infection or other sexually transmitted
    infection (e.g., syphilis), subject will be excluded and may be referred to her
    provider for further management.
  - Document vaginal discharge (quantity, color, odor, and consistency).
  - Document objective signs of inflammation (edema, erythema, excoriation). Inspection and appearance of the cervix, vagina, and vulva, and document presence or absence of objective signs of inflammation (edema, erythema, excoriation).
  - Document vaginal secretion pH testing using pH paper 4-6.
  - Saline "wet mount" for microscopic examination (performed by licensed clinician or laboratory staff certified or trained to read vaginal wet mounts):
    - Document the presence of and percentage of cells that are "clue cells."

- If motile flagellated protozoa are seen, the subject will be excluded from participating in the trial and referred to her provider to be treated using established standards.

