4.4.2. Method of Assigning Subjects to Treatment Groups (Randomization)

Enrollment of subjects is done online using the enrollment module of AdvantageEDCSM. Subjects are randomly assigned to active drug or placebo in a 2:1 ratio. The study uses a stratified, permuted blocked randomization scheme. Permuted block randomization is used to avoid the potential for serious imbalance in the number of subjects assigned to each group during the study, an imbalance that can occur in the simple randomization procedures. Stratification is by clinical site.

The randomization is prepared by statisticians at the Statistical and Data Coordinating Center (SDCC) and included in the enrollment module for the trial. AdvantageEDC assigns each subject to a treatment group after the demographic and eligibility data have been entered into the system.

The vaginal gel applicators are packaged as a kit sufficient for twice daily administration for 3 consecutive days (six applicators). Random kit numbers are provided to Fisher, the investigational product distributor, in order to ensure the associated sets of applicators are filled with the same contents (placebo or active) without unblinding the sites to what treatment is in

each kit once the shipments arrive. Each vaginal gel dispensing kit is individually labeled with the kit number. Once a subject is assigned a randomization number, a kit corresponding to the assigned treatment is distributed to the subject.

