5. SAMPLE SIZE CONSIDERATIONS

The statistical informational goal for the study is 90 subjects eligible for the primary efficacy analysis of clinical cure in the modified Intent-to-Treat (mITT) efficacy population. This is an ad-hoc sample size determined by logistical and feasibility considerations, as there is insufficient pilot data upon which to base more formal sample size calculations.

Subjects who did not meet all inclusion/exclusion criteria, who have a Nugent score <4 at Visit 1 or are positive for other concomitant vulvovaginal infections at baseline which may interfere with the efficacy assessment will be excluded from the mITT population.

Based on observed rates of these outcomes at the participating clinics, it is anticipated that a total of 120 subjects will be enrolled to reach this target. However, enrollment will be continued past 120 subjects to a maximum of 150, if necessary, to reach the informational goal of 90 eligible subjects.

The table below shows the statistical power conferred by this sample size for a two-sided significance level 5% Fisher's exact test comparing binomial proportions, under different assumed proportions.

Power to compare binomial proportions using a two-sided significance level 0.05 Fisher's Exact Test with a sample size of N = 90 (60 subjects in the 5% Monolaurin Vaginal Gel arm, 30 subjects in the Vehicle Placebo Gel arm) is shown below. Conditions in which Power is \geq .80 are highlighted.

	5% Monolaurin Vaginal Gel (N=60)											
		.05	.10	.20	.30	.40	.50	.60	.70	.80	.90	.95
•	.05	.02	.04	.38	.82	.97	>.99	>.99	>.99	>.99	>.99	>.99
(= 3 0	.10	.13	.03	.15	.52	.85	.98	>.99	>.99	>.99	>.99	>.99
el (N	.20	.53	.22	.03	.12	.42	.78	.96	>.99	>.99	>.99	>.99
bo G	.30	.86	.61	.15	.03	.12	.41	.76	.95	>.99	>.99	>.99
lace	.40	.98	.89	.47	.13	.04	.13	.41	.76	.96	>.99	>.99
le P	.50	>.99	.98	.79	.42	.13	.04	.13	.42	.79	.98	>.99
ehic	.60	>.99	>.99	.96	.76	.41	.13	.04	.13	.47	.89	.98
Λ	.70	>.99	>.99	>.99	.95	.76	.41	.12	.03	.15	.61	.86
	.80	>.99	>.99	>.99	>.99	.96	.78	.42	.12	.03	.22	.53
	.90	>.99	>.99	>.99	>.99	>.99	.98	.85	.52	.15	.03	.13
	.95	>.99	>.99	>.99	>.99	>.99	>.99	.97	.82	.38	.04	.02

With respect to the safety objectives, for a sample size of 60 subjects in the treatment arm with no observed SAEs related to study product, the 95% confidence interval (CI) for the estimated proportion is (.00,.06) (Clopper-Pearson interval).

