6.1.1. Pseudo Code

The following SAS® peudo code will be used to calculate the following:

Fisher's Exact test:

```
proc freq;
Table treatment*analysis_variable / exact;
ods output FishersExact=outputdsn1;
run;
```

95% Wilson CI for proportions/percents:

```
Proc freq;
Table treatment*analysisvariable / binomial(wilson);
    ods output binomialcls=outputdsn2;
Run;
```

95% Wilson CI for difference in proportions (produces Newcombe CI):

```
Proc freq;
Table treatment*analysisvariable / riskdiff(cl=Wilson);
Exact Riskdiff;
ods output pdiffcls=outputdsn3;
Run;
```

95% Clopper-Pearson CI for proportions/percents:

```
Proc freq;
Table treatment*analysisvariable / binomial(clopperpearson);
ods output binomialcls=outputdsn2;
Run;
```

95% Exact CI for difference in proportions:

```
Proc freq;
Table treatment*analysisvariable / riskdiff(cl=Exact);
Exact Riskdiff;
ods output pdiffcls=outputdsn3;
Run;
```

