8.1. Primary Efficacy Analysis

The primary efficacy endpoint is the proportion of subjects with clinical cure in each study arm at Visit 2 (Day 8-15), TOC.

A test of hypothesis comparing the proportion of subjects who achieve clinical cure at the Test of Cure Visit, Visit 2 (Day 8-15), will be conducted in the mITT population using the randomized treatment, and repeated as a secondary analysis using the actual treatment received in the PP population and the Evaluable analysis population, and using the randomized treatment in the Intent-to-Treat population. The null hypothesis for each comparison is that there is no difference in proportions of clinical cure between treatment groups, with a two-sided alternative that considers the possibility of a difference in either direction. Fisher's exact test at the 5% two-sided level of significance will be used without adjustment for multiplicity. The number of subjects, the proportion of subjects who achieved clinical cure (clinical cure will be presented for each analysis population and treatment group. In addition, the difference in proportions between the 5% Monolaurin Vaginal Gel arm and the Placebo gel arm and 95% Wilson confidence intervals will be presented. See **Table 29**. See Section 6.1 for pseudocode to fit the above analyses.

A subject listing of individual Amsel criteria will be provided in Listing 22. A summary of Amsel criteria is provided for subjects by visit and site in Table 33. The number of Amsel criteria present (0,1,2,3,4), pH (> 4.5, \leq 4.5), Clue cells (\geq 20%, < 20%), Amine ("whiff") test on KOH wet mount (Positive, Negative), and discharge (yes/no) will be summarized. A summary of Amsel criteria is provided for subjects by visit and treatment group for each analysis population in Tables 34-37. Individual efficacy response data is presented in Listing 10. Reasons for clinical failure are provided in Listing 24.

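### Randomisation is stratified by site but the clinical-cure test is not, and the stated reason for pooling does not cover locally read Amsel criteria; power is lost only if cure rates differ by site

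*SAP*

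**What the plan says.** - **Allocation.** SAP 4.4.2: "Subjects are randomly assigned to active drug or placebo in a 2:1 ratio", in permuted blocks, and "Stratification is by clinical site". Protocol 5.3.1 agrees. The Protocol Summary names three recruiting centres: "Iowa Hospitals and Clinics, Cincinnati Children's Hospital Medical Center and Duke University School of Medicine".
- **Primary analysis.** SAP 8.1 tests clinical cure at Visit 2 in the mITT: "Fisher's exact test at the 5% two-sided level of significance will be used without adjustment for multiplicity". The code in SAP 6.1.1 is a two-way table, "Table treatment*analysis_variable / exact", with no site term. The interval for the difference is an unstratified Newcombe interval. Protocol 11.4 and 11.7.2 also specify Fisher.
- **Pooling.** SAP 6.7: "Safety and efficacy data will be pooled across all clinical sites. Center effects are not anticipated because treatment is self-administered". It adds two further reasons: standardised assessment of unsolicited adverse events, and central Nugent scoring.
- **Endpoint.** SAP 3.3.3 defines clinical cure by discharge, whiff test, clue cells and pH, all normal. A subject also fails if the investigator thinks more treatment is needed. At Visit 1 (Protocol 7.1) the wet mount is "performed by licensed clinician or laboratory staff certified or trained to read vaginal wet mounts"; Protocol 7.2 has a similar requirement at Visit 2. No central reading of these items is described.
- **Other use of site.** SAP 6.4 does not list site as a covariate or subgroup. SAP Table 33 shows Amsel criteria by site but not by arm. SAP 6.7 refers to 8.3 and 9.3 for details, but neither contains a site analysis of clinical cure.

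**The concern.** The usual practice is to analyse by the factor used to stratify allocation, or to explain why not. Here the explanation does not fit the endpoint. Adverse-event procedures are not efficacy. The Nugent score enters bacteriological and therapeutic cure but not clinical cure. Self-administration does not tell us who reads the outcome, or whether the sites recruit similar women. Discharge appearance, odour, clue-cell percentage and the judgement that more treatment is needed all depend on the reader.

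Two things are at stake. One is power, in a trial whose mITT target of 90 rests on feasibility and whose own table gives .76 to .79 for several 30-point differences. The other is a clear headline result, because the planned test and interval can disagree.

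**Working it through.** **Inputs.** Two-sided .05 Fisher test (SAP 8.1). mITT target: "The statistical informational goal for the study is 90 subjects eligible for the primary efficacy analysis of clinical cure". Arms of 60 and 30 (SAP 5). Three sites. Site sizes and site-specific cure rates are not in the documents, so those below are assumptions: 20 active and 10 placebo per site, with a common odds ratio across sites.

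**1. Reproduce the plan's power.** Sum the binomial probabilities over all 61 × 31 possible tables with Fisher p ≤ .05. For .50 vs .20 this gives .783 (SAP .78); .60 vs .30, .765 (.76); .70 vs .40, .760 (.76); .40 vs .10, .869 (.85). Of 121 cells, 115 agree within 2 points. The other six are stated 2.1 to 4.2 points too low, which does not affect this point.

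**2. Separate Fisher's conservatism from stratification.** The stratified comparator is the Cochran-Mantel-Haenszel (CMH) test without continuity correction. With a_i active cures, m_i total cures and arm sizes n1_i and n0_i (total n_i) at site i:

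X² = [Σ(a_i − n1_i·m_i/n_i)]² / Σ[n1_i·n0_i·m_i(n_i − m_i)/(n_i²(n_i − 1))]

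The unstratified Pearson test is the bridge. Fisher to Pearson removes the conservatism; Pearson to CMH shows what stratifying adds. In the last two rows the odds ratio is 4, so active cure at a site is 4p/(1 + 3p): .10 gives .308, .30 gives .632, .50 gives .800, .40 gives .727, .60 gives .857.

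| Pooled cure | Placebo cure by site | Fisher | Pearson | CMH | Exact stratified | CMH − Pearson, points |
|---|---|---|---|---|---|---|
| .50/.20 | equal | .785 | .819 | .813 | .790 | −0.6 |
| .50/.20 | .13/.19/.28 | .788 | .824 | .829 | .794 | 0.5 |
| .50/.20 | .07/.17/.36 | .800 | .836 | .864 | .843 | 2.8 |
| .50/.20 | .04/.14/.42 | .808 | .843 | .901 | .884 | 5.8 |
| .60/.30 | equal | .764 | .771 | .770 | .767 | −0.1 |
| .60/.30 | .20/.29/.41 | .770 | .778 | .796 | .762 | 1.8 |
| .60/.30 | .12/.27/.51 | .782 | .789 | .837 | .800 | 4.8 |
| .60/.30 | .07/.24/.59 | .797 | .802 | .883 | .857 | 8.1 |
| .58/.30 | .10/.30/.50 | .715 | .724 | .789 | not run | 6.5 |
| .63/.37 | .10/.40/.60 | .658 | .679 | .768 | not run | 8.8 |

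These are simulated: 20,000 trials per row (6,000 for the exact test), and 100,000 for the last two rows. Differences use unrounded values. Sites of 45, 30 and 15 subjects gave similar results in the first eight scenarios.

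**3. Type I error.** Fisher is about .037 at a common rate of .20, .026 at .10/.30/.50 and .021 at .10/.40/.60. CMH is .047 to .051.

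**4. Test against interval as planned.** Example: 25/60 vs 6/30, difference .417 − .200 = .217. The Wilson lower limit for 25/60 is .301 and the upper limit for 6/30 is .373. The Newcombe lower limit is .217 − √[(.417 − .301)² + (.373 − .200)²] = .008; the interval is .008 to .381. Fisher p = .059. There are 28 possible tables of this kind and none in the opposite direction. Their probability is 3.4% at .50 vs .20, 5.3% at .45 vs .20 and 5.2% at .40 vs .20. Site does not enter this calculation.

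**5. Would a stratified Newcombe interval match CMH?** Not exactly. With Mantel-Haenszel weights it disagrees with CMH about 0 in roughly 0.9% of trials with equal sites, 6.6% at .10/.30/.50 and 9% at .10/.40/.60. In the last two scenarios every conflict was CMH rejecting while the interval contained 0. The planned pair disagrees in about 3.4%, 0.9% and 2.1% in the same scenarios.

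**The case against.** The case for leaving the plan alone is substantial, and much of it stands.

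- **Validity.** A reader might infer that ignoring the stratification factor invalidates the test. It does not: type I error stayed below .05 in every scenario.
- **Unconditional power loss.** A reader might also infer that power is simply lost. With equal sites nothing is lost by ignoring site. The 3-point gap between Fisher and CMH at .50 vs .20 is Fisher's conservatism, since unstratified Pearson gains as much.
- **Falling Fisher power.** The decline from .78 to .72 to .66 across the odds-ratio-4 scenarios is not the price of pooling. The pooled difference itself shrinks from .30 to .28 to .26, and Fisher power at those pooled rates without any site effect is already .70 and about .64. Only the gap between tests within a row counts.
- **The mismatch.** The disagreement between test and interval comes from pairing Fisher with Newcombe, so stratifying does not remove it; step 5 shows it can become more frequent.
- **Context.** The trial is phase II with a feasibility sample size and no target power. The Amsel definitions are common to all sites, pH and clue cells have numeric cut-offs, and readers are trained. Table 33 will show gross site differences.

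What this does not answer is that SAP 6.7 gives no reason that applies to the primary endpoint, and that no analysis of cure uses the stratum or shows cure by site and arm.

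**Conclusion.** The point holds in a limited form. The design is stratified by site, the primary analysis is not, and the rationale for pooling does not address local Amsel assessment or investigator opinion. The planned test is valid and conservative.

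The cost of ignoring site is nil if cure rates are equal across sites, about 1 point of power for mild differences (0.5 to 1.8 in the table), and about 6 to 9 points for large ones. The large cases rest on assumed spreads such as .10/.30/.50 or .10/.40/.60 with odds ratio 4. The documents neither give nor exclude such differences, so they do not support a claim that power will be lost.

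The test-interval conflict, about 3 to 5% at the rates shown in step 4, is a separate and smaller issue. It would exist without stratification.

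**What to change.** Before unblinding:

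1. Prespecify a site-stratified test of clinical cure in the mITT. Choose either CMH or the exact conditional stratified test now. Do not switch between them on observed counts, which would let the data select the test.
2. Report a site-stratified common risk difference, and name its interval method.
3. Preferably make this the primary test, amend Protocol 11.4 and 11.7.2 to match, and keep unstratified Fisher as a sensitivity analysis. At minimum, make the stratified analysis the prespecified sensitivity analysis.
4. State that the p-value governs if test and interval disagree. This is needed with either pairing, because the stratified interval is not an exact inversion of CMH.
5. Add a table of clinical cure by site and arm.
6. Rewrite SAP 6.7 to address local Amsel reading and investigator opinion. Do not delete it: its reasons still apply to unsolicited adverse events and to Nugent-based results.

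**Cost.** A few lines of code, one table and SAP text, plus a protocol change if the primary test moves. CMH is asymptotic, and equal sites would have only about 10 placebo subjects each; at 10% cure that is one expected cure per site. The exact stratified test avoids the approximation but gains little or nothing over Fisher when site differences are mild (.794 vs .788 and .762 vs .770 above). The Fisher-based power table would become approximate.
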